# 17.2 Determination of Sample Size

Assuming the use of a t-test, with a 2-sided alpha level of 5% and a 30% dropout rate up to Week 48, a sample size of 190 subjects per group (380 subjects in total) will provide 85.5% power to detect a treatment effect size of 0.37 (ie, an absolute treatment difference of 2.6 with an associated standard deviation [SD] of 7) in the change from baseline in ALSFRS-R score to Week 48 between oral edaravone 105 mg dose once daily versus oral edaravone 105 mg dose on/off regimen; see details in Appendix 6.

A sample size of 190 subjects per groups will have 78% power to detect statistically significant result if the true hazard ratio (HR) between edaravone 105 mg daily (test) to edaravone 105 mg on/off regimen (control) is HR=0.3. Namely, 70% risk reduction in the hazard assuming 90% survival rate at Week 48 for the control group. This calculation assumes 2-sided alpha of 5% using the log-rank test and a follow-up time of 48 weeks.

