#### **Decision Making Process**

- When 105 mg oral edaravone and oral placebo once daily will meet this futility rule (ie, Conditional Power < 42.5%), then, Independent Data Monitoring Committee (IDMC) will recommend to "Halt the study due to futility on the primary endpoint".
- The IDMC will also perform interim analysis for secondary efficacy endpoint, other efficacy endpoints, and safety endpoints in an exploratory manner.
- The IDMC will review all endpoints result and recommend the following:
  - o Halt the study if futility is observed or
  - O Continue the study until completion.

As the above interim analysis does not allow the early stopping of the study for proven efficacy and does not allow for dropping arm due to futility, the impact will only be on the type II error so that the Sponsor will use type of I error rate of 1-sided 0.025.

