4. STUDY DESIGN

4.1. Study Design

This is a Phase 3b, multicenter, double-blind, parallel group, randomized, study that will evaluate the efficacy and safety of 2 treatment regimens of edaravone for a period of 48 weeks in subjects with ALS as follows:

- Group 1: Edaravone 105 mg oral dose once daily for 48 weeks
- Group 2: Edaravone 105 mg oral dose in for 14 days, followed by a 14-day placebo. Subsequently, repeat edaravone 105 mg oral dose in for 10 days followed by 18-day placebo (regimen denoted as on/off).

Eligible subjects will be randomized at baseline in a 1:1 ratio to receive 1 of 2 treatment groups. Randomization will be stratified according to ALSFRS-R rate of decline score for 8 weeks screening period (2 levels strata of -1,-2 or -3,-4) and geographical region (3 levels strata of Europe, America or Asia Pacific).

Concomitant use of riluzole is permitted when the doses and regimens will remain unchanged from the day of evaluation of ALSFRS-R at the screening visit, through the end-of-treatment (EOT) or early termination (ET). Although dose reduction, dose interruption or discontinuation due to the onset of AEs, progression of dysphagia, or gastrostomy while on oral edaravone 105 mg are allowed, it is prohibited to initiate the use of riluzole. Subjects who initiate riluzole therapy de-novo during the treatment period will be discontinued from the study. The use of AMX0035 will be allowed for patients in the event that it becomes commercially available via prescription in their respective country. AMX0035 should be taken at least 1 hour after MT-1186.

This study consists of a screening period of 8 weeks, a double blind treatment period of 48 weeks, and a safety follow-up period of 2 weeks. A schedule of assessment of all study procedures is provided in Table 1.

- **Screening period:** Screening assessments will be performed up to 8 weeks (\pm 7 days) prior to Day 1. All screening evaluations must be completed and reviewed to confirm that potential subjects meet all eligibility criteria. If a subject has not met all eligibility criteria at the end of the screening period, the subject will be registered as a screen fail. Screen fail subjects may be eligible for re-screening 1 time.
- **Double-blind Treatment Period:** Subjects who successfully complete the screening period will return to the study clinic on Day 1 in a fasting state (eg, without breakfast) and inclusion

Statistical Analysis Plan
Protocol No. MT-1186-A02

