4.2. Sample Size and Power Considerations

Assuming the use of a t-test, a 2-sided alpha level of 5% and a 30% dropout rate up to Week 48, a sample size of 190 subjects per groups (380 subjects in total) will provide 85.5% power to detect an effect size of 0.37 (ie, an absolute treatment difference of 2.6 with an associated standard deviation [SD] of 7) in the change from baseline in ALSFRS-R score to Week 48 between edaravone 105 mg oral dose once daily versus edaravone 105 mg oral dose on/off regimen; see details in Appendix 1.

A sample size of 190 subjects per groups will have 78% power to detect statistically significant result for the time to death, tracheostomy, or permanent assisted mechanical ventilation. This calculation assumed a true hazard ratio between edaravone 105 mg daily (test) to edaravone 105 mg on/off regimen (control) of $HR=0.3$. Namely, 70% reduction in the hazard assuming 90% survival rate at Week 48 for the control group. This calculation assumes 2-sided alpha of 5% using the log-rank test and follow-up time of 48 weeks.

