5. PLANNED ANALYSIS

5.1. Interim Analysis

One formal interim analysis (IA) for early stopping due to futility will be conducted when the first 133 subjects complete the Week 48 visit, taking into account for the dropout rate of 30% and 50% for total sample size of 380 subjects. The interim futility stopping boundaries were determined using Lan and DeMets O’Brein-Fleming for type II error spending (details are described in Appendix 1).

The Independent Data Monitoring Committee (IDMC) will conduct the IA in unblinded manner and will provide its recommendations (see section 5.3)

A separate SAP for futility analysis will be finalized prior to Interim data lock.

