
Statistical Analysis Plan
Protocol No. MT-1186-A02

Mitsubishi Tanabe Pharma America, Inc.

13. Crispin Jenkinson, Robert Harris & Ray Fitzpatrick (2007) The Amyotrophic Lateral Sclerosis Assessment Questionnaire (ALSAQ-40): Evidence for a method of imputing missing data, *Amyotrophic Lateral Sclerosis*, 8:2, 90-95, DOI: 10.1080/17482960600989343

**APPENDIX 1 INTERIM ANALYSIS SIMULATION RESULT AND DECISION
MAKING PROCESS**

The table below provides the operating characteristics results to Lan and DeMets O'Brein-Fleming stopping boundaries for futility to detect treatment difference at Week 48 when comparing 105 oral edaravone once daily (Test Group) to edaravone 105 mg oral dose on/off (Control Group). The following assumption, using EAST software version 6 were used.

- One sided type I error of 0.025
- Total sample size of 266 completers, taking into account 190 subjects randomized per arm and 30% dropout rate up to Week 48
- Delta of 2.6 units in ALSFRS between Test group to control group with SD of 7.0
- Non-binding for type I error rate
- Lan and DeMets with O'Brein-Fleming beta spending function
- IA time point of 50% of total 266 completers, which yields 133 subjects who completed the Week 48 visit and have ALSFRS data.
- P-value for final analysis of 0.025

The above assumptions yielded a futility Stopping rule boundary of conditional power <42.5% assuming the effect for unobserved data will be the same as alternative hypothesis in the design stage (namely, 2.6).

The Statistical Simulation Result by EAST Software Version 6

Study Plan	True Delta (SD)	Power	Probability to Stop	Average Sample Size
Fixed ^a	2.6 (7.0)	85.5%	No applicable	No applicable
Simulation 1	2.6 (7.0)	84.5%	4.5%	260.1
Simulation 2	2 (7.0)	63.4%	11.3%	250.9
Simulation 3	1 (7.0)	21.1%	35.3%	219.1
Simulation 4	0 (7.0)	2.4%	67.1%	176.8

a. NOTE: SAS software 9.4

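### The sample-size sentences give 85.5% power without saying it is the fixed-design figure; the appendix they cite gives 84.5% when the planned futility rule is followed.

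*SAP*

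**What the plan says.** SAP 4.2 states its conditions first, "Assuming the use of a t-test, a 2-sided alpha level of 5% and a 30% dropout rate up to Week 48", and then claims that 190 per group "will provide 85.5% power to detect an effect size of 0.37", explained as "an absolute treatment difference of 2.6 with an associated standard deviation [SD] of 7". Protocol 17.2 repeats the claim: "will provide 85.5% power to detect a treatment effect size of 0.37". The protocol synopsis carries the same sentence. None of the three mentions an interim look in the power statement, but each sends the reader to an appendix (SAP Appendix 1, Protocol Appendix 6).

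A futility look is part of the design. SAP 5.1: "One formal interim analysis (IA) for early stopping due to futility will be conducted when the first 133 subjects complete the Week 48 visit". Protocol 17.4.5.7 plans the same look.

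The appendix table has a row for a fixed plan, with power 85.5% and with stopping probability and average sample size marked as not applicable. The next row, Simulation 1, has the same difference and SD with the look in place: power 84.5%, probability of stopping 4.5%, average sample size 260.1. Of the look, Protocol Appendix 6 says "the impact will only be on the type II error".

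**The concern.** A reader takes the power in a sample-size section to be that of the planned design, including any stopping rule. Here the sentence uses the fixed-plan row, while the row that includes the planned look is one point lower. A futility rule can only reduce power, because some trials that would have ended in a significant result are stopped at the look. The documents acknowledge that effect, but the headline sentence leaves it out.

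The stakes are small. No decision on sample size, alpha or boundary turns on one point. What is affected is the agreement between the power statement, the interim-analysis section and the appendix.

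**Working it through.** **Inputs**
- Difference 2.6, SD 7 (SAP 4.2). Effect size 2.6/7 = 0.371, given as 0.37.
- Two-sided 5% (SAP 4.2), which is equivalent to "One sided type I error of 0.025" in SAP Appendix 1.
- 1:1 allocation: "Eligible subjects will be randomized at baseline in a 1:1 ratio" (SAP 4.1).
- 190 per arm with 30% dropout: 190 × 0.70 = 133 completers per arm, 266 in total (SAP Appendix 1).
- Look at 133 of 266 completers, information fraction t = 0.5. Stop if conditional power is below 42.5%, taking 2.6 as the effect in the unobserved data (SAP Appendix 1).

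**Step 1. Reproduce 85.5% (no look)**
- Noncentrality = 2.6 / (7 × √(2/133)) = 3.029.
- Two-sample t-test, 264 degrees of freedom, two-sided 5%: power **85.50%**, matching the stated figure.
- Normal approximation: Φ(3.029 − 1.960) = Φ(1.069) = **85.75%**.

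**Step 2. Convert the futility rule to a boundary on the interim Z**
- Conditional power under 2.6 is 1 − Φ[(1.960 − z₁√t − 3.029(1 − t)) / √(1 − t)].
- Setting it to 0.425 gives z₁ = [1.960 − 1.514 − 0.7071 × 0.1891] / 0.7071 = 0.441.
- As an observed difference at the look: 0.441 × √(2 × 49/66.5) = 0.54 points.

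**Step 3. Power with the rule followed**
- Probability of stopping = Φ(0.441 − 3.029 × 0.7071) = Φ(−1.701) = 4.45%.
- Average sample size = 266 − 133 × 0.0445 = 260.1.
- Power = P(Z₁ ≥ 0.441 and Z₂ ≥ 1.960), bivariate normal with means 2.142 and 3.029 and correlation √0.5: **84.46%**.

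| True difference | Power, plan | Power, recomputed | Stop, plan | Stop, recomputed |
|---|---|---|---|---|
| 2.6 | 84.5% | 84.5% | 4.5% | 4.4% |
| 2 | 63.4% | 62.8% | 11.3% | 11.4% |
| 1 | 21.1% | 20.5% | 35.3% | 35.1% |
| 0 | 2.4% | 2.4% | 67.1% | 67.0% |

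A seeded simulation of 400,000 trials at a difference of 2.6 gave 84.4% with a z-test at the final analysis and 84.2% with a t-test.

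**Step 4. Size of the gap**
- On the plan's figures: 85.5 − 84.5 = 1.0 point (type II error 15.5% instead of 14.5%).
- Both on the normal scale: 85.75 − 84.46 = 1.29, about 1.3 points. The plan's two figures come from different tools, SAS for the fixed row and EAST for the simulations, so their difference is not a clean estimate of the loss.
- For scale only: by the normal approximation, reaching 85.5% with the rule followed needs about 137 completers per arm. That is 137/0.70 = 196 randomized per arm, 392 in total against the planned 380.

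**The case against.** The case for leaving the text alone has four parts.

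- **The sentence is right on its own terms.** It assumes a t-test, 5% alpha and 30% dropout, and those inputs give 85.50%. This stands: no figure is wrong.
- **The loss is disclosed.** The same sentence cites the appendix, where both rows sit together, and the protocol says that the look affects type II error. This also stands, and a reader who inferred that the loss was hidden would be mistaken. But someone sent to the appendix for details of 85.5% finds it attached to a fixed plan, with nothing in the power sentence to say so.
- **The committee is not bound.** The boundary is non-binding for type I error, and the committee reviews all endpoints before recommending. A reader might infer that 85.5% belongs to a trial that will not take place. The documents do not support that: if the rule is always overridden, power returns to 85.5%. They do say that the committee will recommend halting when conditional power falls below 42.5%, so 84.5% is the power under the rule as written.
- **One point is within the uncertainty of the inputs.** By the normal approximation, SD 7.1 instead of 7.0 lowers power from 85.7% to about 84.8%, and 32% dropout instead of 30% lowers it to about 84.7%. This is a sound reason to leave the sample size alone. It does not explain quoting the fixed row without a label.

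**Conclusion.** The point holds as a minor matter of labelling. The 85.5% is correctly calculated for a fixed design, and the sample-size sentences present it without that condition. With the planned look and the rule followed, the plan's own simulation gives 84.5%, which the recomputation confirms. The overstatement is 1.0 percentage point on the plan's figures and about 1.3 points by the normal approximation.

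This rests on the plan's own assumptions: a true difference of 2.6, SD 7, exactly 30% dropout and a look at half the information. Depending on how often the rule is followed, power lies between 84.5% and 85.5% on the plan's figures.

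A reader might also take 84.5% as the power of the current primary analysis. It is not. Both figures concern the ALSFRS-R change, and SAP 3.2.1 and 9.2.1.1 now make CAFS at Week 48 primary.

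**What to change.** In SAP 4.2, Protocol 17.2 and the protocol synopsis, state that 190 per group gives 84.5% power for the ALSFRS-R change if the planned futility boundary is followed, and 85.5% for a fixed design without the look. Keep the reference to the appendix. In SAP 4.2, add that neither figure is the power of the CAFS analysis.

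The cost is one clause in each of three places and one short sentence in the SAP. Both numbers are already in the appendix, so no new calculation is needed. Sample size, boundary and analysis do not change.

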5. PLANNED ANALYSIS

5.1. Interim Analysis

One formal interim analysis (IA) for early stopping due to futility will be conducted when the first 133 subjects complete the Week 48 visit, taking into account for the dropout rate of 30% and 50% for total sample size of 380 subjects. The interim futility stopping boundaries were determined using Lan and DeMets O’Brein-Fleming for type II error spending (details are described in Appendix 1).

The Independent Data Monitoring Committee (IDMC) will conduct the IA in unblinded manner and will provide its recommendations (see section 5.3)

A separate SAP for futility analysis will be finalized prior to Interim data lock.

5.2. Final Analysis

The final analysis related to the primary, secondary and exploratory objectives will be performed when all subjects complete Week 48 or the safety follow up period.

The Database will be locked according to Mitsubishi SOP GLB-DMG-SOP001 after the sign off the current SAP.

5.3. Data Monitoring Committee (DMC)

An IDMC is a multidisciplinary group comprised of medical/clinical experts and a biostatistician, all external to the sponsor. The IDMC will review unblinded IA results for early

stopping due to futility and unblinded safety data periodically, at predefined intervals, during the study. Any such reviews of study data will be undertaken in accordance with predefined rules and procedures. These rules will be implemented to ensure that access to details of the study blind, and to unblinded data, is carefully controlled. A charter will guide the timing of reviews, communications between the IDMC, the Investigators, and the Sponsor, and stopping rules for the study. In general, the IDMC will advise the Sponsor regarding possible changes to the protocol or study procedures to protect the subjects enrolled in the study.

The IDMC will conduct the IA in an unblinded manner when the first 133 total subjects complete the Week 48 visit, taking into account for the dropout rate of 30% and 50% for total sample size of 380 subjects and will make 1 of 2 recommendations: 1) Halt the study if futility is observed or 2) Continue the study to its completion. The IDMC will communicate their recommendation to the Sponsor.

The specific details including one futility interim stopping and safety data monitoring about the IDMC will be included in an IDMC charter.

6. ANALYSIS POPULATIONS

The statistical analysis will be based on separate analysis sets, defined as follows:

6.1.1. Randomized Set

The randomized set is defined as all randomized subjects. The subjects will be grouped by the planned treatment allocation (as randomized).

6.1.2. Efficacy Full Analysis Set (FAS)

The FAS is defined as all randomized subjects who received at least 1 dose of study medication. Subjects in the FAS will be grouped and analyzed based on the planned treatment allocated (as randomized). Efficacy endpoints will be analyzed using the FAS.

6.1.3. Safety Analysis Set (SAF)

The SAF is defined as all randomized subjects who received at least 1 dose of study medication. Subjects will be grouped and analyzed based on the actual treatment received. Safety endpoints will be analyzed using the SAF by treatment group.

6.1.4. Exploratory biomarker Analysis Set (Ex-biomarker Set):

The Ex-biomarker Set is defined as all randomized subjects who received at least 1 dose of study medication and had any biomarker data collected after dosing. Biomarker endpoints will be analyzed using the Ex-biomarker Set

6.1.5. Exploratory Nerve conduction test Analysis Set (Ex-nerve Set):

The Ex-nerve Set is defined as all randomized subjects who received at least 1 dose of study medication and had any %CMAP, MUNIX, SNAP, and/or SNCV analysis after dosing. Nerve conduction test endpoints will be analyzed using the Ex-nerve Set.

6.1.6. Pharmacokinetic (PK) Population:

PK population includes all subjects who receive at least 1 dose of oral edaravone and who have at least 1 post-dose value for plasma concentration without important protocol deviations which may affect the PK of oral edaravone.

6.1.7. Interim Analysis Full Analysis Set (IA)

The IA set is defined as the first 190 subjects randomized in MT-1186-A02 and who received at least 1 dose of study medication. Subjects in the IA set will be grouped and analyzed based on the planned treatment allocated (as randomized). The data provided to DMC for the futility analysis will be analyzed using the IA set.

7. STATISTICAL CONSIDERATIONS**7.1. Descriptive Statistics**

All data from all subjects randomized into the study will be included in patient data listings.

The listings will be sorted by center and subject number (and by visit, if applicable). An additional listing will be provided for screening failures.

Continuous data will be summarized descriptively using the number in the analysis set (N), the number of observations (n), mean, SD, median, minimum and maximum. Categorical data will be summarized using frequency counts and percentages. The denominator for the percentages will be the total number of subjects in the treatment group and analysis set being presented, unless otherwise specified. For visit-specific data, the number of subjects with non-missing observations at the visit in question will be used as the denominator for percent calculations. Unknown, Not Done, Not Applicable and other classifications of missing data will not be considered.

7.2. Statistical Tests

Unless otherwise specified, all statistical tests will be done as 2-sided at the 5% significance level. Point estimates of treatment differences will be accompanied with 2-sided 95% confidence intervals (CIs) where applicable.

7.3. Type I Error Control

The family-wise type I error of 5% will be maintained for the primary endpoint and key secondary endpoints. To control the overall type I error rate for multiple comparisons across the primary endpoint and the key secondary endpoints, the fixed sequence procedure will be applied. The testing order are described in section 9.2.1.4

Denote:

- H_0x as the null hypothesis to be rejected for each analysis.
- Edaravone 105 mg oral dose once daily for 48 weeks as Treatment group 1
- Edaravone 105 mg oral dose on/off as Treatment group 2

1. H_{01} : There is no treatment difference between Treatment Group 2 and Treatment Group 1 in CAFS at Week 48
2. H_{02} : There is no treatment difference between Treatment Group 2 and Treatment Group 1 in change from baseline to Week 48 in %SVC
3. H_{03} : There is no treatment difference between Treatment Group 2 and Treatment Group 1 in change from baseline to Week 48 in ALSAQ40
4. H_{04} : There is no treatment difference between Treatment Group 2 and Treatment Group 1 in time to death, tracheostomy, or permanent assisted mechanical ventilation (≥ 23 hours/day)
5. H_{05} : There is no treatment difference between Treatment Group 2 and Treatment Group 1 in time to death or permanent assisted mechanical ventilation (≥ 23 hours/day)
6. H_{06} : There is no treatment difference between Treatment Group 2 and Treatment Group 1 in time to death

Hypothesis H_{01} for the primary analysis will be tested at a significance level of 5%. In order to protect the study from type-I error inflation, the first key secondary endpoints will be interpreted inferentially only if H_{01} is found significant. Type-I error will be further controlled

for the key secondary endpoints (H02 – H06) when each will be analysed only in case the preceding endpoint will have a p-value less or equal to 0.05.

8. DATA CONVENTIONS

8.1. Baseline Definition

In general, Baseline will be defined for each subject as the last available, valid, non-missing assessment obtained prior to the first date of study drug administration. The analyses involving calculation of change from baseline will be based on the actual changes from baseline (not percentage), unless stated otherwise.

8.2. Data Handling Convention for Missing Data

In general efficacy data will not be imputed unless otherwise noted.

For safety summaries, only observed data will be used. Unless otherwise specified, missing safety data will not be imputed. For each analysis variable, how to handle missing data are described in section 8.3 respectively.

8.3. Handling of data for PK assessment

PK data that are considered "invalid" will be flagged in the listing. The PK data handling will be assessed after unblinding and a PK data handling assessment record will be produced.

8.4. Analysis Variable Definitions

8.4.1. Study Subjects Measures

8.4.1.1. Protocol Deviation

Protocol deviations will be identified and documented during a blinded data review meeting prior to database lock and confirmed by database lock. The major protocol deviations will be selected in this meeting. At least the following major protocol deviations will include:

I/E criteria violation

Taking prohibited concomitant medications except for AMX0035

Test/Procedure performed by non-study trained or experienced staff for ALSFRS-R
etc

